We propose a pilot clinical trial on the use of perioperative pregabalin in order to decrease ureteral stent related symptoms and decrease opioid usage after ureteroscopy with stent placement. Patients undergoing ureteroscopy with stent placement will receive a single dose of 300 mg pregabalin PO in the preoperative area. We will assess safety and feasibility of studying this regimen at our institution, with the aim of performing a randomized, placebo-controlled, double-blinded study in the future.

OBJECTIVES AND SCIENTIFIC AIMS

Primary Hypothesis

It is safe and feasible to study perioperative pregabalin in ureteroscopy with stent placement at our institution.

Exploratory Hypotheses

We hypothesize that the use of the perioperative pregabalin will:

- decrease ureteral stent related symptoms at 3 days post-op
- decrease the probability of a patient requiring narcotic pain medication
- decrease the total amount of narcotic pain medication used
- decrease the unplanned contact between the patient and the healthcare system related to the stent
- improve patient satisfaction after ureteroscopy with stent placement

Primary Endpoints

The primary endpoints will be as follows:

- Adverse events related to study drug
- Verified correct administration of study drug
- Correct use of study instruments

Secondary Endpoints:

Secondary endpoints include the following:

- Ureteral Stent Related Symptom Questionnaire (USSQ) [1] score at 3 days post op
- Monitored prescribing of narcotic pain medication
- Number of patients taking narcotic pain medication at several time points
- Oral morphine equivalents the patient has used at several time points
- Number of unplanned contacts between the patient and the healthcare system within 30 days
- Score on standardized evaluation of patient satisfaction

BACKGROUND AND STUDY DESIGN/INTERVENTION

The prevalence of urolithiasis is greater than 8% and increasing in the United States (US) [2]. There are several treatment options, including ureteroscopy (with or without laser lithotripsy), extracorporeal shock wave lithotripsy, and percutaneous nephrolithotomy. A recent study in California demonstrated that ureteroscopic treatment was employed in more than 40% of interventions [3], with some nationwide estimates up to 59% [4]. At least 300,000 stone

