Routine evaluation and management for those undergoing ureteroscopy with stent placement include:

ASA classification, assigned by the anesthesiologist

Deep venous thrombosis prophylaxis per standardized pathway

Estimated blood loss

Use of intraoperative fluids (crystalloid, colloid, blood products)

TOXICITIES/SIDE EFFECTS

Various symptoms have been associated with the administration of pregabalin in the perioperative setting. The risk of serious adverse events in this use of pregabalin is low [25] and the potential benefits of this treatment may outweigh the risks. This will be recorded in the PACU side effect and PACU nursing questionnaires.

Surgical complications will be assessed prospectively and retrospectively and reviewed using the institutional standard for complications reporting for all surgical patients as followed by the Department of Surgery. Standardized graded complications and adverse effects at UM utilize the five-point modified Clavien-Dindo system. Grade I include complications requiring monitoring but no intervention; Grade II requires bedside or medical treatment; Grade III constitute adverse events requiring surgical or procedural intervention with return to normal functioning; Grade IV includes disabling, life-threatening complications with resulting functional loss and grade V is death of the patient. This is a modification of the Clavien-Dindo system for reporting complications with defined, categorized and classified events that will be segregated into time periods of ≤ 30 days, 31-90 days and > 90 days after surgery and includes medication complications following NCI CTCAE version 5 guidelines.

CRITERIA FOR THERAPEUTIC RESPONSE/OUTCOME ASSESSMENT

If the surgery is aborted for any reason before placement of a ureteral stent, the patient will be removed from the study and replaced. Based on past experience these issues are rare events.

The intraoperative period is defined as the period from anesthesia induction to the extubation of the trachea. The surgical time is determined from the incision to the final skin closure.

The postoperative period is defined as the period from the extubation to various study endpoints.

Blood loss is defined as the estimate accounted from the suction device and absorptive sponges during the procedure, as described and agreed upon by the surgeon, anesthesiologist, circulating nurse, and surgical technician as covered by institutional guidelines.

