The experimental intervention (perioperative pregabalin administration) is currently used at University of Missouri Hospital through the ERAS protocol. Numerous studies have shown significant patient benefits in all fields, including Urology. Several reviews have demonstrated the efficacy and safety of perioperative gabapentinoid administration. The principal side effects of pregabalin are temporary cognition/coordination changes, with a very low risk of serious side effects. Therefore, we do not believe that the therapeutic aspects of this trial pose any serious risk different from patients undergoing ureteroscopy with stent placement under standard procedures.

Toxicities and side effects

Adverse outcomes are not anticipated with the regimen of pregabalin used in this study. Patients are closely monitored during the perioperative period and any serious events will be immediately brought to the attention of the study staff. All potential side effects will be recorded in questionnaires.

Alternatives / Therapeutic options

The alternative to participation in the trial would be to undergo ureteroscopy with stent placement according to the surgeon's standard practice and not to participate in the study. The

patient may or may not receive pregabalin in this case. No other aspect of patient care would differ.

Financial Costs and Burdens

Subjects will not be compensated for their participation. The cost involved in this study is study medication and administration. As these are potentially part of standard treatment, these will be billed to patients as other hospital charges.

Privacy and Confidentiality

We will keep the study records confidential. No identifiers will be used in any reports or publications resulting from the study.

Volunteering Nature of the Study

Participation is entirely voluntary. All aspects of patient's care and monitoring will be unaffected by whether the patient chooses to consent for the study.

Serious Adverse Event (SAE) Reporting

Any SAE will be reported to the IRB as soon as possible, but no later than 5 calendar days. The reporting procedure will be followed as outlined in the University of Missouri protocol found in the "Core Standard Operating Procedure for Event Reporting."

INFORMED CONSENT PROCEDURES

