
- Yes
- No

On what side was ureteroscopy performed?

- Right
- Left
- Bilateral
- None

Was the patient extubated in the OR?

- Yes
- No

What was the planned disposition for the patient?

[figure not shown]
- Home from PACU
- Floor
- ICU

Pacu Discharge

At one hour post op: How much pain is the patient in?

No pain

Most pain

(Place a mark on the scale above)

Where is the patient going after PACU discharge?

- Home from PACU
- Floor
- ICU

How long was it (in minutes) from when the patient arrived in the PACU until they went home?

Please indicate if the patient experienced any of the following since surgery. A check indicates that the patient did experience this adverse event.

	Yes
Dizziness	
Vertigo	
Incoordination	
Balance disorder	
Ataxia	
Diplopia	
Blurred vision	
Amblyopia	
Tremor	
Somnolence	
Confusional state	
Disturbance of attention	
Thinking abnormality	
Euphoria	
Edema	
Peripheral edema	
Asthenia	
Fatigue	
Dry mouth	
Constipation	
Amnesia	
Back pain	
Contusion	
Depersonalization	
Diarrhea	
Fall	
Headache	
Hyperhidrosis	
Increased appetite	
Infection	
Memory impairment	
Nausea	
Nervousness	
Neuropathy	
Pain	
Paresthesia	
Sinusitis	

Upper RTI

Vomiting

What are the patient's expectations regarding post-operative pain?

- There will be minimal pain regardless of treatment
- The pain regimen being given for discharge will be sufficient
- More pain medication will be required

What pain control does the patient believe they will need in addition?

- Opioid pain medication
- Non-opioid pain medication only

Aldrete

Time to Aldrete 9 or 10:

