(Number of minutes from arrival in PACU to modified Aldrete score of 9 or 10. In 15 minute increments)

Early patient questionnaire

Date form was filled out:

How satisfied are you with your urology team?

- very dissatisfied dissatisfied
 satisfied very satisfied

How satisfied are you with your pain control as related to your urologic procedure?

- very dissatisfied dissatisfied
 satisfied very satisfied

Do you still have a stent in place?

- No
 Yes - the one from your initial surgery on [surg_date]
 Yes - the stent is from a different procedure

How satisfied are you with your stent related symptoms?

- very dissatisfied dissatisfied
 satisfied very satisfied

Please tell us the pain medications you have taken since surgery. For each, please list the name of the medication, the dosage, and the total number. Use a new line for each new medication.

Evaluation of trial

Please complete the survey below.

Thank you!

84) Date: _____

85) Evaluator is: Patient
 Treatment Doctor
 Treatment Nurse
 Study Staff

86) What could be done to make the study better? Was there anything important to you that was not evaluated? _____

Evaluation of trial PACU nurse

Date:

What could be done to make the study better? Was there anything important to you that was not evaluated?

30 Days Post Op Study

How many pills of oxycodone 5mg did the patient have prescribed?

What other narcotics was this patient prescribed? Please include the name of the narcotic along with dosage and number of pills.

How many total ED visits or hospitalizations did the patient have?

How many ED visits or hospitalizations did the patient have related to their ureteroscopy?

How many contacts with the urology team did the patient have?

For how many days was the stent in place? Indicate 31 for stent still in place at 30 days post-op.

Unanticipated Contact

Date of unanticipated contact:

What kind of unanticipated contact did you have with the patient?

- Phone
- Email or chart message
- Regularly scheduled clinic appointment
- In clinic but not at a regularly scheduled appointment
- In the emergency department
- As an inpatient
- Other

What was the unanticipated contact?

Was this related to stent discomfort?

- Yes
- No

Was pain medication prescribed?

- Yes - an NSAID was prescribed
- Yes - the study opioid was prescribed
- Yes - another opioid was prescribed
- Yes - another pain medication was prescribed
- No

What was the other pain medication prescribed?

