Appendix 3 – Aldrete

PACU Discharge form

Subject ID: _____

Baseline BP: ____ / ____

Date: ____ / ____ / ____

Record the first Aldrete score at 15 min and take off O2 mask

Aldrete	15 min	30 min	45 min	60 min	75 min	90 min	115 min	120 min	Comments
Respiration									
O2 Saturation									
Consciousness									
Circulation									
Activity									
Total									

Time when Aldrete score is 9 or 10: ____ : ____ (record time or call anesthesia attending)

Chart 1. The 'modified' Aldrete Scale			
RESPIRATION	2	1	0
	Able to take deep breath and cough	Dyspnea/Shallow Breathing	Apnea
O2 SATURATION	2	1	0
	Maintains > 92% on room air	Needs O2 inhalation to maintain O2 saturation > 90%	Saturation < 90% even with supplemental O2
CONSCIOUSNESS	2	1	0
	Fully awake	Arousable on calling	Not responding
CIRCULATION	2	1	0
	BP ± 20mmHg pre op	BP ± 20-50mmHg pre op	BP ± 50mmHg pre op
ACTIVITY	2	1	0
	Able to move 4 extremities voluntarily or on command	Able to move 2 extremities voluntarily or on command	Able to move 0 extremities voluntarily or on command

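### The PACU adverse event checklist is closed and starts at surgery, so a non-serious allergic, respiratory, blood pressure or unlisted event can be missing from the reported adverse effect proportions

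*Protocol*

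**What the plan says.** Under Protection of Human Subjects (Toxicities and side effects), the protocol states that "All potential side effects will be recorded in questionnaires". Its Toxicities/Side Effects section says of symptoms associated with perioperative pregabalin: "This will be recorded in the PACU side effect and PACU nursing questionnaires". The first primary endpoint is "Adverse events related to study drug". Proposed Analyses lists serious, all and drug-related adverse events, and the SAP will describe the share of patients reporting possible adverse effects.

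The forms are printed in the appendices:

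- **Pacu Discharge (Appendix 1).** A tick-box list introduced by "Please indicate if the patient experienced any of the following since surgery".
- **Aldrete (Appendix 1, REDCap).** One field, a time: "Number of minutes from arrival in PACU to modified Aldrete score of 9 or 10. In 15 minute increments".
- **Aldrete sheet (Appendix 3).** Five domains charted in columns from 15 to 120 minutes, with baseline blood pressure and a comments column. It carries the instruction "Record the first Aldrete score at 15 min and take off O2 mask".

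Toxicities/Side Effects also describes a modified Clavien-Dindo grading of complications that takes in medication complications under CTCAE version 5. Serious adverse events go to the IRB.

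**The concern.** The promise is that every potential side effect reaches a questionnaire. A closed list can show only what is printed on it. If an event has no box, no free-text line and no other database field, it drops out of the reported proportion without trace, and the blank form looks the same as that of a patient with no event.

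Safety is half of the pilot's primary hypothesis, and the result is meant to inform a later randomized trial. With about 10 completers and no control group, the safety conclusion rests almost wholly on what the forms can record.

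**Working it through.** No power or sample size figure bears on this. The check sets the printed forms against the promise.

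**1. Content of the checklist.** Counting the Pacu Discharge items gives 39.

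| Type of event | Items out of 39 |
|---|---|
| Acute respiratory (apnea, dyspnea, respiratory depression) | 0 |
| Oxygenation | 0 |
| Blood pressure | 0 |
| Allergic reaction (allergy, rash, hives) | 0 |
| Other / free text | 0 |

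The nearest entries are Upper RTI and Sinusitis, which are not acute breathing events. Edema could be ticked for swelling but would not identify an allergic reaction. Allergy to gabapentinoids is an exclusion criterion, so the protocol itself recognises that type of event. Each item has a single yes box, with no onset, grade or relatedness.

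**2. Window.** The dose is given about one hour before surgery (Pre-op standardized care). The checklist asks about the time since surgery. On its wording, the interval from dosing to surgery is outside the window.

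**3. What the Aldrete time preserves.** The total is the sum of five domains, each scored 0 to 2, so the maximum is 10.

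- One domain at 1 and four at 2: 1 + (4 × 2) = 9, which meets the threshold.
- Two domains at 1 and three at 2: (2 × 1) + (3 × 2) = 8, which does not.
- One domain at 0 and four at 2: 0 + (4 × 2) = 8, which does not.

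The threshold can therefore be met while one domain is at 1. By the Appendix 3 chart, that domain could be shallow breathing, a blood pressure 20 to 50 mmHg from the pre-operative value, or the oxygen item: "Needs O2 inhalation to maintain O2 saturation > 90" percent. A long time to threshold does not show which domain was low. The sheet has room for 5 domains × 8 columns = 40 domain scores per patient; REDCap takes one time.

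**4. Other routes by which such an event could be recorded.**

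| Route | What it captures | What it leaves open |
|---|---|---|
| Appendix 3 sheet | Respiration, saturation, consciousness, circulation, comments | Domain scores have no REDCap field and are not defined as adverse events |
| Graded complications (Clavien-Dindo/CTCAE) | Non-serious events too; Grade I needs monitoring only | No Appendix 1 form holds the grade |
| SAE reporting | Serious events | Non-serious events |
| Evaluation of trial, PACU nurse | Free text on improving the study and on what was not evaluated | No adverse event field |
| Early patient questionnaire, days 3 and 7 | Satisfaction, stent status, pain medication | No adverse event question |
| Late patient questionnaire, from day 30 | Unrecorded issues related to the procedure | Late, and not directed at the drug |
| Unanticipated Contact | Events that lead to a contact | Depends on a contact occurring |

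**5. Size of one missed event.** The protocol plans 10 completers and estimates 20 enrolled. One event is 1/10 = 10% of completers or 1/20 = 5% of those enrolled. If it has no box and is the only event of its kind, the reported figure is 0%. This is illustrative: the documents give no expected frequency for these events.

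**The case against.** The strongest reply is that much is already covered. The documents name temporary cognition and coordination changes as the principal side effects, and the checklist covers these heavily: dizziness, ataxia, somnolence, confusional state, disturbance of attention. It also lists fall, nausea and vomiting. The Appendix 3 sheet is a scheduled trial record of breathing, saturation and circulation. The grading scheme reaches non-serious medication complications. All of this stands, and it limits the point.

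A reader might go further in four ways that the documents do not support:

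- **That acute drug harms have no scheduled place at all.** They do, on the checklist and on the Appendix 3 sheet. The gap concerns particular types of event and their path into the reported data. Absence from REDCap is also not absence from the trial record, since source documents are kept.
- **That the missing events are those most relevant to a single dose of pregabalin.** Nothing in the documents ranks them so. An Aldrete form is a recovery score, not evidence of drug risk.
- **That a patient at 9 is recorded as recovered.** The field records a time to a score, and discharge has its own separate criteria.
- **That the PACU nursing questionnaire must be the feedback form.** The schedule of questionnaires also gives a nurse as respondent for the PACU form and the Aldrete form, so the term may mean either. On any of these readings, no printed form supplies an allergic item or an open adverse event line.

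An added oversedation item would largely repeat Somnolence. Counting every domain score below 2 as an adverse event would capture ordinary emergence from general anaesthesia. Neither is recommended.

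**Conclusion.** The point holds in limited form. The promise that all potential side effects reach a questionnaire is not met by the printed forms. Four types of event have 0 of 39 items, there is no open line, and the window starts after the dose. For breathing, oxygenation and blood pressure, the gap is between the paper sheet and the database. For allergic and unlisted events, no adverse event field exists at PACU discharge. The graded complication route could recover such events, but nothing printed shows how its grades enter the data behind the SAP's proportions.

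The consequence is possible under-reporting of non-serious events in a primary endpoint, by 5 to 10 percentage points per missed event on the planned numbers. This assumes that the Appendix 1 forms are the complete set of REDCap instruments and that the SAP's proportions are drawn from them. It does not show that any event would occur or that the study is unsafe. It is a worthwhile correction to the forms, not a defect in the design.

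**What to change.** Change the forms and add one sentence to the SAP:

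1. Add to Pacu Discharge an open line, *Other adverse event (specify)*, with onset, grade and relatedness to study drug. This also gives the grades described under Toxicities/Side Effects a place for events entered there.
2. Add three items: allergic reaction; breathing difficulty or unplanned oxygen need; low blood pressure. The circulation score cannot supply the last, because it does not separate a fall from a rise.
3. Change the checklist window to run from the time the study drug was given.
4. Enter the Aldrete domain scores already charted into REDCap. State in the SAP that they will be reported descriptively by time point, and not as adverse events in themselves.

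No new patient assessment is needed and no treatment changes. The cost is three check boxes, one open line and transcription of at most 40 scores per patient (5 × 8), or 400 for 10 patients and 800 for 20. More events will be listed, and some will reflect anaesthesia rather than the study drug. Without a control group the two cannot be separated, and the report should say so.

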Appendix 1 – REDCap instruments

Appendix 2 – USSQ

Appendix 3 – Aldrete

Appendix 4 – Post-op study specific instruction

Appendix 5 – Written consent and HIPAA authorization

Appendix 6 – HIPAA waiver of authorization

Appendix 1 – REDCap instruments

Screening questionnaire

Study identifier:

What is the patient's age?

Before this episode, did the patient have a ureteral stent in place?

Yes
 No

Before this episode, did the patient use narcotic pain medications at home on a regular basis? This includes medications such as Percocet, Norco, tramadol, and others.

Yes
 No

Has the patient ever had an issue with addiction or dependence to narcotic pain medication?

Yes
 No

Does the patient take gabapentin or pregabalin at home?

Yes
 No

Has the patient ever had an issue with addiction or dependence to gabapentin or pregabalin?

Yes
 No

Has the patient ever had an allergic reaction to gabapentin or pregabalin?

Yes
 No

Is the patient pregnant or is there any possibility the patient could be pregnant?

Yes
 No

What is the patient's eGFR?

Is the patient comfortable consenting to this procedure in English?

Yes
 No

Is there a pharmacy we can send the patient's prescriptions to electronically?

Yes
 No

Does the patient have a phone number they can be reached at regularly?

Yes
 No

Does the patient want to participate want to be excluded from this study?

Yes
 No

This patient is not eligible for this study

Baseline Surgery

Surgery date:

Medical record number:

Last name:

First name:

Date of birth:

What is the patient's gender identity?

- Male
 Female
 Other

What is the indication for procedure?

- Stone disease
 Diagnosis of stricture
 Diagnosis/treatment of tumor
 Other

What side is the procedure predicted to be done on?

- Right
 Left
 Bilateral

What is the patient's preferred phone number?

Would the patient be comfortable getting email reminders to fill out surveys?

- Yes
 No

Email is not a fully secure method of transmitting information. If someone intercepts an email from us, they may know that the patient is participating in this trial.

- Yes
 No

Knowing this, would it be okay for us to contact the patient by email with survey reminders?

What is the patient's email address?

What kind of pain control does the patient anticipate they will need at home after the procedure?

- Opioids
 Non-opioid pain control only

Post-op Surgeon

On what side was a stent placed?

- Right
- Left
- Bilateral
- None

Was a string left on the stent?

- Yes
- No

On what side was ureteroscopy performed?

- Right
- Left
- Bilateral
- None

Was the patient extubated in the OR?

- Yes
- No

What was the planned disposition for the patient?

[figure not shown]
- Home from PACU
- Floor
- ICU

Pacu Discharge

At one hour post op: How much pain is the patient in?

No pain

Most pain

(Place a mark on the scale above)

Where is the patient going after PACU discharge?

- Home from PACU
- Floor
- ICU

How long was it (in minutes) from when the patient arrived in the PACU until they went home?

Please indicate if the patient experienced any of the following since surgery. A check indicates that the patient did experience this adverse event.

	Yes
Dizziness	
Vertigo	
Incoordination	
Balance disorder	
Ataxia	
Diplopia	
Blurred vision	
Amblyopia	
Tremor	
Somnolence	
Confusional state	
Disturbance of attention	
Thinking abnormality	
Euphoria	
Edema	
Peripheral edema	
Asthenia	
Fatigue	
Dry mouth	
Constipation	
Amnesia	
Back pain	
Contusion	
Depersonalization	
Diarrhea	
Fall	
Headache	
Hyperhidrosis	
Increased appetite	
Infection	
Memory impairment	
Nausea	
Nervousness	
Neuropathy	
Pain	
Paresthesia	
Sinusitis	

Upper RTI

Vomiting

What are the patient's expectations regarding post-operative pain?

- There will be minimal pain regardless of treatment
- The pain regimen being given for discharge will be sufficient
- More pain medication will be required

What pain control does the patient believe they will need in addition?

- Opioid pain medication
- Non-opioid pain medication only

Aldrete

Time to Aldrete 9 or 10:

(Number of minutes from arrival in PACU to modified Aldrete score of 9 or 10. In 15 minute increments)

Early patient questionnaire

Date form was filled out:

How satisfied are you with your urology team?

- very dissatisfied dissatisfied
 satisfied very satisfied

How satisfied are you with your pain control as related to your urologic procedure?

- very dissatisfied dissatisfied
 satisfied very satisfied

Do you still have a stent in place?

- No
 Yes - the one from your initial surgery on [surg_date]
 Yes - the stent is from a different procedure

How satisfied are you with your stent related symptoms?

- very dissatisfied dissatisfied
 satisfied very satisfied

Please tell us the pain medications you have taken since surgery. For each, please list the name of the medication, the dosage, and the total number. Use a new line for each new medication.

Evaluation of trial

Please complete the survey below.

Thank you!

84) Date: _____

85) Evaluator is: Patient
 Treatment Doctor
 Treatment Nurse
 Study Staff

86) What could be done to make the study better? Was there anything important to you that was not evaluated? _____

Evaluation of trial PACU nurse

Date:

What could be done to make the study better? Was there anything important to you that was not evaluated?

30 Days Post Op Study

How many pills of oxycodone 5mg did the patient have prescribed?

What other narcotics was this patient prescribed? Please include the name of the narcotic along with dosage and number of pills.

How many total ED visits or hospitalizations did the patient have?

How many ED visits or hospitalizations did the patient have related to their ureteroscopy?

How many contacts with the urology team did the patient have?

For how many days was the stent in place? Indicate 31 for stent still in place at 30 days post-op.

Unanticipated Contact

Date of unanticipated contact:

What kind of unanticipated contact did you have with the patient?

- Phone
- Email or chart message
- Regularly scheduled clinic appointment
- In clinic but not at a regularly scheduled appointment
- In the emergency department
- As an inpatient
- Other

What was the unanticipated contact?

Was this related to stent discomfort?

- Yes
- No

Was pain medication prescribed?

- Yes - an NSAID was prescribed
- Yes - the study opioid was prescribed
- Yes - another opioid was prescribed
- Yes - another pain medication was prescribed
- No

What was the other pain medication prescribed?

The patient's disposition will be:

- Home - they do not need to be evaluated
- Clinic - they will be in clinic in the next 3 business days for evaluation
- Emergency department - they require evaluation in the emergency department
- Hospital - they will be directly admitted
- Other

What is the patient's disposition?

Does this constitute something that should be brought to the attention of the study physicians?
In addition to submitting this form, you must email the study physicians

- Yes
 - No
- (Examples would include: serious adverse event related to study medication, serious change in health status, serious patient concern)

Late patient questionnaire

Date form was filled out:

Do you regularly take narcotic pain medication?

- Yes
- No

Have you had any issues related to your procedure on [surg-date] that has not yet been recorded?

- Yes
- No

Please describe the issue:

USSQ

Date completed:

Urinary index score:

Pain index score:

General health index score:

